Optical Head-Mounted Display Technology for Low Vision Rehabilitation

NCT02983305

June 15, 2018

PROTOCOL

1. Background

Worldwide it is estimated that 191 million people have moderate to severe visual impairment (MSVI) and an additional 32.4 million are blind (1). Patients with uncorrectable MSVI may undergo low vision rehabilitation (LVR), which has been shown to improve functional abilities, such as mobility (2). However, existing LVR strategies do not adequately address severe visual field constriction, and much of the evidence that points toward improved functional performance from LVR is based on patient self-report (3). Accordingly, there is a **critical barrier** to improving and measuring function among patients with severe visual field constriction that we seek to address.

In this pilot study, we will test the **hypothesis** that optical head-mounted display technology expands constricted visual fields and improves mobility and quality-of-life. While there are many causes and forms of visual impairment, our **objective** is to assess optical head-mounted display technology in LVR for patients with severely constricted visual fields resulting from retinal dystrophy.

Objectives/Specific Aims

We will test our hypothesis in the following aims:

Primary Aims

1. To demonstrate that optical head-mounted display technology increases the planimetric area of the visual field.

Other Aims

2. To quantify the impact of optical head mounted display technology on mobility using gait and head movement analyses.
3. To measure the impact of optical head mounted display technology on vision-related quality of life and self-reported function.

1. Methods

a. Study Design

Demographic data, medical history, laboratory results, medications and clinical information will be extracted from the medical record, including visual acuity and results of visual field, electroretinogram, ultrasound, optical coherence tomography, MRI and CT.

Participation in the study will occur on two separate days 2-4 weeks apart.

Upon enrollment all participants will complete:

- Measurement of height, weight and limb length
- Measurement of visual acuity and contrast sensitivity
- Full ophthalmologic examination including intraocular pressure measurement, slit lamp biomicroscopy and indirect ophthalmoscopy
- Goldmann visual field examination
- Windows tablet visual field examination
- Electroretinogram (if not done in year prior to enrollment; only done by patients, not controls)
- Impact of Vision Impairment Questionnaire (4) and Independent Mobility Questionnaire (6)
- Mobility testing, as detailed in below (Aim 2)

Participants will be fit with HMD technology (Epson Moverio www.epson.com/moverio; **Figure 2**) and undergo a brief training with the investigators to learn about use of the device and will receive materials describing how to charge the device and turn it on and off. While wearing the device the subjects may have some discomfort related to the weight of the device on the ears and/or nose. The nose piece can be adjusted with pads for optimal comfort. A band on the arm pieces of the frame can also be adjusted for comfort. Initially, there may be the sense of disorientation, may feel dizzy or nausea, but with coaching/training the subject is anticipated to adapt. In order to adapt to the technology, participants will be permitted to bring the HMD home to use (for 2-4 weeks).

When participants return after a period of adaptation to the HMD, they will undergo the following:

- Impact of Vision Impairment Questionnaire (4), Independent Mobility Questionnaire (6), and the System Usability Scale (12)
- Videotaped open-ended interview in which subjects will be asked to describe their experience using HMD and to discuss any challenges and successes using the technology.
- Goldmann visual field and tablet visual field examination (while wearing the HMD)
- Mobility testing, as detailed below (Aim 2; while wearing the HMD)

To accomplish Aim 1 we will use the following approaches:

After the period of in-home adaptation, participants will return to have their visual field retested with Goldmann perimetry after a period of adaptation to the technology. We predict the outcome of increased planimetric area of the peripheral vision determined by Goldmann perimetry.

To accomplish Aim 2:

We propose to collect and analyze gait and head movement parameters in order to provide a quantitative analysis of mobility-associated factors of persons with severe visual field constriction and controls with and without the use of optical head-mounted display technology. We will mount an inertial measurement unit (IMU) data logger (Actigraph GT9X "Link", <http://www.actigraphcorp.com/products/actigraph-link/>; **Image 2**) on the patients' shoe; it will be placed inside a small pouch that rests on top of the shoe laces. A second IMU device will be mounted on

the frames of the patients' existing glasses (or on a mock frame if the patient does not wear glasses) in order to measure head pitch, roll and yaw. The subjects will be asked to walk around a long empty corridor during which time they will be timed and videotaped and IMU data will be acquired. Then, participants will be asked to walk the same corridor after obstacles are arranged in the corridor every 1-2 meters. Obstacles will be short pieces of foam lying on the floor, knee to waist high cardboard boxes, or pieces of foam hanging from the ceiling. A research assistant will follow close to participants in order to provide assistance should this be required. Testing mobility in the presence of obstacles is important in order to more closely approximate real-world scenarios. Video recording is essential in order to correlate aberrancies in IMU data with obstacles in the patients' environment. The same procedure will be repeated with the patients wearing optical head-mounted display technology after the period of in-home adaptation to the technology with the device turned off (to serve as a negative control) and with the device turned on.

To accomplish Aim 3:

Participants will all complete the Impact of Vision Impairment and Independent Mobility Questionnaire at the time of their enrollment in the study. These surveys will be completed again after the period of in-home adaptation to the OHMD. We will also analyze qualitative data collected through open-ended interviews after use of HMD.

We will conduct statistical analyses, as detailed in Section 2e, to describe associations between outcomes assessed throughout our Aims.

b. Eligibility

Participants with retinal dystrophy will be recruited into this study from the Retinal Dystrophy Clinic in the Department of Ophthalmology and Visual Sciences at the University of Michigan.

Normal controls will be included to adjust for the baseline impact of HMD on visual fields and gait parameters and to compare these to data from patients with RP. Comparing to a group of age-matched control patients will allow us to investigate and understand the true impact of HMD on visual fields, gait, and quality of life. Control participants will be recruited from the Comprehensive and Pediatric Ophthalmology Services at the University of Michigan. We will seek to enroll up to 40 subjects in order to obtain ten patients and ten age-matched controls with complete data, allowing room for those who don't complete both study visits and technical errors with equipment.

Criteria

Inclusion criteria for subjects with retinal dystrophy:

- diagnosis of retinal dystrophy
- severe vision loss that constitutes legal blindness
- able to perform a reliable Goldmann visual field test
- constricted visual field less than or equal to 20 degrees by Goldmann perimetry using the III4e stimulus in at least one eye with best-corrected visual acuity $\geq 20/60$

Inclusion criteria for control subjects:

- healthy controls
- able to perform a reliable Goldmann visual field test

Exclusion criteria for subjects with retinal dystrophy:

- movement disorder that precludes evaluation of mobility
- functional vision loss
- pregnant women

Exclusion criteria for control subjects:

- visually significant ocular condition other than correctable refractive error
- movement disorder that precludes evaluation of mobility
- functional vision loss
- pregnant women

c. Study Setting

Patients will be recruited from the Retinal Dystrophy Clinic of the Department of Ophthalmology and Visual Sciences at the University of Michigan; controls will be recruited from the Comprehensive and Pediatric Clinics of the Department of Ophthalmology and Visual Sciences at the University of Michigan. Study exams, clinical testing, surveys and interviews will be completed in the Kellogg Clinical Research Center. Mobility testing will be conducted in a hallway located in the Kellogg Clinical Research Center.

d. Outcome measures

Primary Outcome Measures:

- Change in the planimetric area of Goldmann visual field with the use of head-mounted display technology compared to baseline (measured in degrees squared):
Using computer software we will calculate the area of participants' Goldmann visual fields in order to obtain a summary quantitative measurement of the extent of peripheral vision.

Secondary Outcome Measures:

- Change in gait speed compared to baseline (measured in seconds):
Gait speed will be measured using an inertial measurement unit attached to participants' shoes and will quantify the time taken to move from the beginning to end of a short mobility course.

Other Outcome Measures:

- Change in patient-reported ability for independent mobility as assessed by subject responses a validated questionnaire:
Independent Mobility Questionnaire (scored from 35 to 175 with 175 representing extreme mobility impairment)
- Change in patient-reported mobility and independence as assessed by subject responses a validated questionnaire:
Mobility and Independence domain of the Impact of Vision Impairment Questionnaire (scored from 0 to 33 with 0 representing poor mobility and independence)
- Change in stride length compared to baseline (measured in mm):

Inertial measurement units attached to participants' shoes will track the length of each step as they walk through a short mobility course.

- Change in stride width compared to baseline (measured in mm):
Inertial measurement units attached to participants' shoes will track the width of each step as they walk through a short mobility course.
- Change in foot orientation compared to baseline (measured in degrees):
Inertial measurement units attached to participants' shoes will track the orientation of their feet as they walk through a short mobility course.

e. Planned Data Analysis

To address Aim 1 the visual field will be assessed before and after being trained to use optical head-mounted display technology. The Goldmann visual field plots will be scanned and the planimetric areas for each stimulus size will be measured using Adobe Photoshop CC (San Jose, CA) as previously described (8). In brief, using a scale of 10 degrees on the visual field, the corresponding number of pixels are determined, and the units are set to millimeters. Areas are measured in mm² using the Magic Wand tool and are converted to degrees squared. Areas of scotomas are subtracted from the total area. We will analyze the change in area before and after a 2-4 week period of adaptation to the OHMD. The adaptation period is important as it will allow subjects to become familiar with how to use the device and to gain insight into how using such a device may impact their life. The Mann-Whitney U test will be used to compare change in visual field area between patients and controls.

To address Aim 2 we will measure change in gait speed with and without the use of OHMD. We will calculate percent preferred walking speed to compare the ratio of gait speed measured in the presence and absence of physical obstacles. We will also use our data processing algorithms to reconstruct the paths of the feet and head movements during the planned experiments from which we can estimate mobility parameters (9–11). For gait, we will gather measures of stride length, width and period, and their variabilities, from straight-line walking, lateral/foot-angle relation, stride frequency, ground contact time, etc. For head movement we will gather measures of head pitch, head roll and head yaw. The mean and standard deviation of each gait and head movement parameter will be compared before and after being trained to use optical head-mounted display technology (11,12). We will use Wilcoxon signed-rank test to test for significant differences. Significant changes (and trends) will be assessed for direction and magnitude, and resulting values will be compared to gait and head movement parameter norms before and after using the optical head mounted display. The Mann-Whitney U test will be used to compare changes in gait parameters between patients and controls.

To address Aim 3 we will use the Wilcoxon signed-rank test to determine whether individual participants' survey scores changed from baseline when using optical head mounted display technology. We will also use the Mann Whitney U test to compare changes in survey scores between patients and controls. Cohen's d will be calculated to measure the overall effect size of the intervention as measured by the surveys. Minimum clinically important differences will also be calculated (ratio of change in visual ability to 1.95 standard errors of the measured change) to determine if changes in each individual's visual ability were clinically important.

We will also calculate Spearman correlations between variables (visual field area, mobility parameters and survey results) and use multiple regression to investigate associations while controlling for covariates.

Image 1. The Epson Moverio® Head Mounted Display.

Image 2. The Actigraph Link Inertial Motion Unit.

References

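### Where the head sensor sits at visit 2, and how it is re-zeroed, is not stated, so the before/after test of mean head angles may count a change of mounting angle as a device effect

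*Combined protocol and SAP*

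**What the plan says.** The relevant text is in Study Design (the visit lists and the Aim 2 paragraph) and in Planned Data Analysis (the Aim 2 paragraph).

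- **Baseline mount.** The head sensor goes on "the frames of the patients' existing glasses (or on a mock frame if the patient does not wear glasses"; the purpose is "in order to measure head pitch, roll and yaw".
- **Visit 2.** The visit list has "Mobility testing, as detailed below (Aim 2; while wearing the HMD", and the Aim 2 paragraph says "The same procedure will be repeated with the patients wearing optical head-mounted display technology", once switched off as a negative control and once switched on.
- **The headset.** It is itself a frame resting on nose and ears: "The nose piece can be adjusted with pads for optimal comfort", and "A band on the arm pieces of the frame can also be adjusted for comfort".
- **Analysis.** "The mean and standard deviation of each gait and head movement parameter will be compared before and after being trained", with the Wilcoxon signed-rank test. The resulting values are also to be set against norms.

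Three things are not stated: whether the sensor stays on the glasses or mock frame or moves to the headset at visit 2; any alignment, zeroing or reference posture for it; and any analysis of the device-off walk. The Mann-Whitney comparison of patients with controls in the Aim 2 paragraph names gait parameters only. Head angles do not appear under Outcome measures.

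**The concern.** A sensor fixed to a frame records the tilt of the frame. That equals the tilt of the head plus the angle at which the frame and sensor sit on the head. If the second term is the same at both visits, it drops out of the before/after difference. If it changes, the difference contains the change.

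Visit 2 gives it reason to change. If the sensor moves to the headset, the mount is a different object. If it stays on the glasses or mock frame, that frame is refitted 2-4 weeks later and shares the nose and ears with the headset. A single headset design could shift the angle in the same direction for most wearers.

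At stake is the reading of mean head pitch, roll and yaw. A changed mean could be reported as changed head posture when only the mounting had changed. The same offset would carry into the comparison with norms. A missing reference posture cannot be added after the walks are done.

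**Working it through.** The plan gives no SD, effect size, alpha or power for head angles, so it has no figure to reproduce.

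**Inputs from the documents**
- 10 patients with complete data (Eligibility).
- Paired before/after comparison of means, Wilcoxon signed-rank (Planned Data Analysis).

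**Inputs assumed**
- Two-sided 5% level.
- Per-walk SD of a person's mean angle: 3 degrees.
- Person-to-person scatter in the mounting change: s = 2 or 4 degrees.
- Common mounting offset: 0, 1, 2, 3 or 5 degrees.
- No true device effect.

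**Step 1: what the difference contains.** Write a walk's recorded mean as true mean + mounting angle m + error. Then

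after − before = true change + (m2 − m1) + (e2 − e1).

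With no true change, its mean is the common offset and its variance is 3² + 3² + s² = 18 + s².
- s = 2: variance 22, SD 4.69 degrees.
- s = 4: variance 34, SD 5.83 degrees.

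**Step 2: the test.** With n = 10, the exact two-sided signed-rank test rejects when the smaller rank sum is 8 or less. Its true size is 50/1024 = 4.88%.

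**Step 3: simulated rejection rates with no true effect** (normal differences)

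| Common offset | s = 4 | s = 2 |
|---|---|---|
| 0 degrees | about 5% | about 5% |
| 1 degree | about 8% | 9% |
| 2 degrees | 16% | 22% |
| 3 degrees | 30% | 42% |
| 5 degrees | 66% | 83% |

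**Step 4: sensitivity to the SD.** If 3 degrees is instead the SD of the difference before remounting scatter, the variance is 9 + s², so the SD is 3.61 (s = 2) or 5.00 (s = 4). The rates rise to about 38-63% at 3 degrees and 79-97% at 5 degrees. Over a wider grid (SD of change 3 to 8 degrees, offset scatter 0 or 3 degrees), a 2-degree offset gives 9.8-45.2% and a 5-degree offset 36.7-99.5%.

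**Step 5: what is not affected**
- *Mounting changes that average zero.* At offset 0 the rate stays near 5% whatever the scatter. Such changes add noise only.
- *Within-walk standard deviation.* SD(x + c) = SD(x). In a simulated walk, adding 5 degrees left it at 6.09.
- *Device on minus device off at visit 2.* If the mount is untouched, m2 is in both walks and cancels. The simulated rejection rate on the wider grid is 4.7-5.1%.
- *Patients versus controls on change.* If the offset has the same distribution in both groups, it cancels. The rate on the same grid is 4.0-4.6%.

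**The case against.** The strongest reply is that this is a gap in description, not a demonstrated bias. The documents never say the sensor moves. Repeating the same procedure could mean the same frame, and the remarks on nose pads and band concern the comfort of the headset. The analysis relies on cited processing algorithms that may include an alignment step. Baseline frames differ between people, so part of any mounting change is individual and would only add noise. The design already includes a device-off walk with the headset on, and controls who wear the same headset. Every angle in the calculation is assumed.

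Most of this stands, and it rules out three stronger readings that a reader might infer.

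- *That the comparison is certainly biased, or that no walk has a neutral reference.* The documents are silent on the visit 2 mount and on zeroing. What can be said is that neither is stated, and that only a shift in a common direction biases the test.
- *That mean head angles cannot be interpreted at all.* The device-off walk gives a contrast free of the offset if the mount is left alone between walks.
- *That the trial's main results are at risk.* The primary outcome is visual field area and the secondary is gait speed; neither uses the head sensor.

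The reply does not close the gap. Keeping the same frame does not guarantee the same angle when a headset shares its seat. No alignment step is stated for the head sensor, and separating head tilt from sensor tilt needs a reference posture or an equivalent assumption. The two safeguards are not connected to this comparison: Planned Data Analysis gives the device-off walk no analysis, and its patient-control test for Aim 2 names gait parameters only.

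**Conclusion.** The point holds as a conditional risk. A before/after test of mean head angles is planned while the visit 2 mount and any re-zeroing are unstated, so a systematic mounting shift could not be told apart from a device effect.

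The size depends wholly on an offset that the documents do not give. Under the main assumptions above, 1 degree does little (about 8-9% false significance), 3 degrees is serious (30-42%) and 5 degrees dominates (66-83%). The planned comparison of standard deviations is essentially sound on this point.

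Head movement analysis is named in Aim 2, but head angles are outside the listed outcomes of a pilot study. The plan should be changed because the remedy is cheap; the study's main conclusions do not depend on it.

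**What to change.** 1. **Planned Data Analysis, Aim 2.** Make device-on versus device-off at visit 2 the contrast for mean head pitch, roll and yaw, and require the sensor mount to be left untouched between those walks.
2. **Study Design, Aim 2 procedure.** State where the head sensor is mounted at visit 2. Before every walk (baseline, visit 2 off, visit 2 on), have the participant stand for 5-10 seconds facing a fixed mark at eye height.
3. **Baseline versus visit 2.** Express each walk's mean angles as deviations from its own standing reference. If no reference is taken, limit this comparison to the standard deviations.

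**Cost.** A few seconds per walk and one processing step; the walks needed for item 1 are already planned. There are two real losses. On versus off does not capture the effect of simply wearing the headset. Referencing to a standing pose adds some noise and removes any posture change already present when standing.

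### The order of the visit-2 device-off and device-on walks is neither specified nor balanced; run as listed, device-on is always last and on-versus-off mixes the device effect with practice or fatigue

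*Combined protocol and SAP*

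**What the plan says.** All locations are in the Methods of the combined protocol and SAP.

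- **Visits** (section a, Study Design): "Participation in the study will occur on two separate days 2-4 weeks apart". The first mobility walks are done at enrolment without the display. The device-worn walks are done after the home adaptation period.
- **Course** (section a, Aim 2): an empty corridor comes first. "Then, participants will be asked to walk the same corridor after obstacles are arranged in the corridor every 1-2 meters".
- **Device conditions** (section a, Aim 2): the procedure is repeated after adaptation "with the device turned off (to serve as a negative control) and with the device turned on".
- **Secondary outcome** (section d): "Change in gait speed compared to baseline (measured in seconds").
- **Analysis** (section e, Aim 2): "To address Aim 2 we will measure change in gait speed with and without the use of OHMD". The mean and SD of each gait and head parameter "will be compared before and after being trained to use optical head-mounted display technology". "We will use Wilcoxon signed-rank test to test for significant differences". Changes in patients and controls are compared by Mann-Whitney U.

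Nowhere do the documents give a rule for the off/on order, a practice walk, a rule on changing the obstacle layout, or a period or order term.

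**The concern.** The device-off walk is the plan's own negative control. It shares with the device-on walk the visit, the weight and obstruction of the frame, and the weeks of adaptation, so it is the natural reference for what the display itself does to gait in a given patient. It serves that purpose only if off and on do not differ systematically in sequence.

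If the walks are run as listed, each participant reaches the device-on walk having just covered the same corridor with the device off. Anything that changes with repetition is then credited to the device. Familiarity would flatter it; tiredness would count against it. Time through an obstacle course could plausibly move either way. A fixed order cannot be undone at analysis, because order and device condition would be the same variable.

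**Working it through.** **Inputs from the documents.** Ten patients and ten controls with complete data (section b); the signed-rank test within person and Mann-Whitney U between groups (section e). The plan gives no significance level, SD or practice effect, so it has no figure of its own to reproduce.

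**Assumptions.** Two-sided 5% level; normal paired differences with SD 1; true device effect δ = 0; the second visit-2 walk is better than the first by g SDs of the paired difference, whichever condition comes first; on-minus-off at visit 2 is the quantity tested.

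**Model.** Let D be the improvement from off to on in one participant.

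- Fixed order, off then on: D = δ + g + e, so the mean is δ + g and the bias is all of g.
- Balanced order, five each way: D = δ + g + e in five and δ − g + e in five. The mean is δ + (5g − 5g)/10 = δ, so the bias is 0.

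**Test.** With n = 10 there are 2^10 = 1,024 sign patterns. The exact two-sided test rejects when the smaller rank sum is 8 or less, and its true level is 50/1,024 = 4.88%.

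**Within-patient false-positive rate** (40,000 simulated trials per setting):

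| Assumed g (SD) | Fixed order | Balanced 5/5 |
|---|---|---|
| 0.3 | 13.4% | 4.1% |
| 0.5 | 28.3% | 3.0% |
| 0.8 | 60.2% | 1.4% |
| 1.0 | 78.5% | 0.7% |

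With g = 0 the fixed-order rate is 4.7%, as it should be. A separate run of 100,000 trials gave 28.2% and 78.5% in fixed order at g = 0.5 and 1.0. In that run essentially all rejections at g of 0.5 or more favoured the device. A negative g (fatigue) gives the same rates in the opposite direction.

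**Why the balanced rate falls below 5%.** The order effect widens the spread of the differences: their mean square about δ goes from 1 to 1 + g², which is 1.09 at g = 0.3, 1.25 at 0.5 and 2.00 at 1.0. The unadjusted test is therefore conservative. An analysis that includes order would recover the loss.

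**Patients versus controls** (Mann-Whitney, 10 v 10, fixed order, no device effect, 20,000 trials per setting):

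| Patient g (SD) | Controls gain the same | Controls gain half | Controls gain nothing |
|---|---|---|---|
| 0.25 | 4.5% | 5.2% | 6.9% |
| 0.5 | 4.3% | 7.0% | 16.4% |
| 0.75 | 4.2% | 10.6% | 32.2% |
| 1.0 | 4.2% | 16.0% | 51.2% |

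**Change from baseline.** Every device-on walk comes 2-4 weeks after the visit-1 walks. Device-on minus baseline therefore contains practice between visits whatever the off/on order.

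**The case against.** Five objections have force.

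1. **No sequence is fixed.** A reader might infer that the plan prescribes off first and so makes device-on always the most practised walk. The text does not go that far. It joins the two conditions with a plain conjunction, while the same paragraph marks a real sequence (empty corridor, then obstacles) explicitly. What stands is that the order is unspecified and unprotected. Left to staff, it can settle into the listed order, and nothing requires it to be recorded.

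2. **The plan never names an on-versus-off test.** The secondary outcome is change from baseline, and the Aim 2 text does not say whether the without-device state means baseline or device-off. The rates for a fixed order therefore belong to a contrast assumed here. This stands, and it shows a related gap: a negative control is collected but given no stated place in the analysis. It also means that balancing alone would not free the stated outcome from practice.

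3. **The control group helps.** Practice common to both groups cancels in the comparison of changes, and the rate stays near 4%. Practice that differs between sighted controls and patients with severely constricted fields does not cancel, and controls do nothing for the within-patient test.

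4. **Obstacle familiarity is assumed.** The plan does not say that the layout is the same on each run. In addition, percent preferred walking speed is a ratio of obstacle to no-obstacle speed, so a change that scales both speeds equally drops out of it. Practice specific to the obstacles does not.

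5. **Size and direction are not known.** Nothing in the documents anchors the practice gain, which here is only the increment between two walks after earlier exposure at visit 1. Fatigue could reverse the sign.

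**Conclusion.** The point holds as a design weakness that is cheap to remove. The off/on order is not specified, randomised or counterbalanced. If the walks are run as listed, on-versus-off cannot separate the device effect from practice or fatigue, and the negative control loses much of its value.

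The range of about 13% to 79% illustrates what a fixed order could do. It is not an estimate of this trial's error rate: it rests on the assumed gains of 0.3 to 1.0 SD, a 5% level, normal differences, a fixed order actually being followed, and a test that the plan does not name. The bias is the full gain g under a fixed order and zero under a 5/5 split, provided the gain is the same in either order. If it is not, half the difference between the two gains remains.

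This is a pilot, mobility is listed under its other aims, and the primary visual field outcome is untouched. The point deserves correction, but it does not threaten the main result.

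**What to change.** - **Order.** At visit 2, randomise or alternate off-then-on and on-then-off, separately within patients and within controls, and record the order for each participant.
- **Layout.** Rearrange the obstacles between runs to a layout of similar difficulty.
- **Contrast.** Name device-on minus device-off at visit 2 as a within-person gait-speed contrast, tested by signed-rank and shown by order. Showing it by order would reveal a gain that depends on which condition came first.
- **Baseline outcome.** Keep the stated change from baseline, say that it still includes practice between visits, and say which state the without-device wording refers to.

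**Cost.** A few sentences in the protocol, a short allocation list and moving the foam and boxes between runs. No walks or equipment are added. The downsides are one more reported contrast and some extra variance in the unadjusted paired difference. That variance is small if the order effect is small, and an analysis that includes order recovers it.

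### The only test named for Aim 1 compares absolute field-area change between capped patients and full-field controls, so it can favour the device when patients gain nothing or lose field

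*Combined protocol and SAP*

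**What the plan says.** The Eligibility section gives the reason for enrolling controls: "Normal controls will be included to adjust for the baseline impact of HMD on visual fields and gait parameters". The same sentence adds a second purpose, comparison with the patients. The two sets of criteria differ sharply on field size:

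- A patient needs a "constricted visual field less than or equal to 20 degrees by Goldmann perimetry using the III4e stimulus in at least one eye".
- A control must be healthy, and is excluded for any "visually significant ocular condition other than correctable refractive error".

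The primary outcome is "Change in the planimetric area of Goldmann visual field with the use of head-mounted display technology compared to baseline (measured in degrees squared"). Under Study Design, baseline perimetry precedes the fitting of the headset, and the return visit lists "Goldmann visual field and tablet visual field examination (while wearing the HMD"). A negative-control condition, "with the device turned off (to serve as a negative control) and with the device turned on", is described for the mobility walk and not for perimetry.

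For Aim 1, Planned Data Analysis says that the before/after change in area will be analysed, and then names one test: "The Mann-Whitney U test will be used to compare change in visual field area between patients and controls". Wilcoxon signed-rank is named for Aims 2 and 3 only. No percent change, common region or baseline adjustment is given for the Aim 1 comparison.

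**The concern.** The comparison is meant to help isolate what the headset does to the field, but the entry criteria put the two groups on very different parts of the area scale. If the frame or display obstructs field beyond a patient's residual island of vision, the control loses that area and the patient has nothing there to lose. The patient's possible III4e loss in the qualifying eye is also bounded by a small baseline, while a control can lose many times as much.

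A patient–control difference can therefore arise from the criteria alone. Aim 1 sets out to demonstrate that the device enlarges the field, and the only p-value planned for it could be very small when the device does nothing for patients or removes some of their field. Treating the control loss as an adjustment would credit the device with field it did not create.

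**Working it through.** The plan gives no alpha, power, effect size or normal field area, so there is no stated figure to reproduce.

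**Inputs from the protocol:** cap of 20 degrees on III4e in at least one eye (whether diameter or radius is not stated); outcome in degrees squared; target of ten patients and ten controls with complete data.

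**Assumed:** normal III4e area 8,000–14,000 deg2; the share of a control's field that the headset blocks, varied below; two-sided 0.05.

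**1. Largest possible patient loss.** An eye cannot lose more than its baseline area. For a circular field:
- 20 degrees as diameter: π × 10² = 314 deg2
- 20 degrees as radius: π × 20² = 1,257 deg2

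**2. Blocking at which a control ranks below every such patient**, even one who loses the whole field:
- Diameter: 314/14,000 = 2.2% to 314/8,000 = 3.9%
- Radius: 1,257/14,000 = 9.0% to 1,257/8,000 = 15.7%

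**3. Consequence for the test.** If all ten controls pass that point, separation is complete. The exact two-sided Mann-Whitney p is 2/C(20,10) = 2/184,756 = 0.000011, in the device's favour.

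**4. Equal proportional loss, no benefit.** Take a control field of equivalent radius 60 degrees: π × 60² = 11,310 deg2. A 10% loss is 1,131 deg2 in the control, against 31 deg2 (diameter) or 126 deg2 (radius) in a patient at the cap. The test reads this as a patient advantage.

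**5. Simulation.** There were 2,000 runs per setting, ten per group. Patient field radius was uniform from half the cap to the cap, and every patient lost 5–25% of field. Control equivalent radius averaged 50, 60 or 70 degrees (7,854–15,394 deg2), with a 3% retest SD. Share of runs with a significant result favouring patients, across both readings of the cap:

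| Control field blocked | Runs favouring patients |
|---|---|
| 0% | 0–4% |
| 2% | 9–44% |
| 5% | 89–98% |
| 10% or 20% | 100% |

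With an equal 10% loss in both groups, the test favoured patients in 100% of runs. When patients lost 5–25% and controls 10% but change was analysed as a percentage, it favoured patients in 0%. The false result therefore comes from the absolute scale.

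**6. The paired view of the same patients.** A signed-rank test on patients alone showed the loss in every run. This follows by construction: ten losses out of ten give p = 2/2¹⁰ = 0.002.

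**The case against.** - **Where and how much the headset blocks is not documented.** The protocol describes no optics, frame obstruction or display position. A reader might infer that controls can never adjust for the headset, or that a false positive is assured. The documents do not support that: blocking in the central field affects both groups, and with almost none in controls the artefact vanishes. This stands. The protocol does, however, itself anticipate some headset effect on the field.
- **The bound is narrow.** A reader might take 314 deg2 as the limit for every patient measurement. It holds only for a circular III4e field in the qualifying eye with 20 degrees read as a diameter. The other eye and other stimuli are uncapped, areas are to be measured for each stimulus size, and the plan does not say which eye or stimulus is primary. This weakens the thresholds but not the mismatch of scale.
- **A loss in patients would not be hidden.** A reader might infer that universal loss could pass unnoticed. The primary outcome is change from baseline, the plan says that change will be analysed, and it predicts an increase, so a loss would show. This stands too. What is missing is a named within-patient test for Aim 1.
- **No decision hangs on the p-value.** This is a pilot without a success rule, controls also serve plain comparison, and no subtraction of control change is specified. That limits the harm. The result would still be the only named inferential result for the primary aim.

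**Conclusion.** The point holds in a conditional form. The patient–control difference in absolute area is not evidence of field expansion, and the control change does not estimate the headset's effect in patients.

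How far the test misleads depends on two quantities that the documents do not give, the normal field area and the share blocked. Under the assumed areas, the point at which a control falls below any capped patient is about 2–4% blocking on the diameter reading and 9–16% on the radius reading. In the simulated settings, where patients lose only part of their field, 5% blocking was already enough to favour patients in most runs on either reading.

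The point concerns the visual field comparison only; the mobility walk has its own device-off condition. It is worth correcting because the correction is nearly free.

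**What to change.** In Planned Data Analysis (section e):

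- Make the within-patient before/after change in area the Aim 1 analysis, tested by the Wilcoxon signed-rank test already used for Aims 2 and 3.
- State that the patient–control difference in total area is descriptive and is not evidence of field expansion.
- Report the controls' change separately, as the amount of normal field the headset blocks.

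In Eligibility (section b), amend the wording about adjustment to match.

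A control change measured within the central region may be shown as a descriptive sensitivity analysis only. It is not a fair comparator: controls start at or near the ceiling there and can essentially only lose, while patients can gain anywhere. It also inherits the unresolved diameter/radius question.

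The cost is a few sentences, with no change to recruitment, visits or sample size. The optional central-region analysis needs one further measurement on control plots already scanned. The small downside is that the between-group p-value no longer supports the primary aim.
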